6.1. Primary Objective

The primary objective of this study is to demonstrate the value of multiple modalities and sustained clinically significant pain relief in patients with chronic pain when using the Boston Scientific Spectra WaveWriter Spinal Cord Stimulator (SCS) System.

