10.1. Point of Enrollment

A subject will be considered enrolled in the study when the Informed Consent Form (ICF) is signed. All enrolled and activated subjects will be included in the study analyses.

If device implantation is unsuccessful, the subject will be followed for 2 weeks post implantation attempt to assess for procedure related adverse events.

10.2. *Withdrawal*

All subjects enrolled in the clinical study (including those withdrawn from the clinical study or lost to follow-up) shall be accounted for and documented. If a subject withdraws from the clinical investigation, the reason(s) shall be reported. If such withdrawal is due to problems related to investigational device safety or performance, the investigator shall ask for the subject's permission to follow his/her status/condition outside of the clinical study.

While study withdrawal is discouraged, subjects may withdraw from the study at any time, with or without reason and without prejudice to further treatment. In all cases of withdrawal or discontinuation, the Investigator will make all reasonable efforts to determine the reason for the subject's withdrawal. Subjects may be discontinued from the study for the various reasons, such as:

- Withdrawal of consent
- A safety concern defined by the Principal Investigator and/or Boston Scientific Neuromodulation (e.g., adverse event)
- Study non-compliance
- Inadequate use of device that may impact study outcomes Subject did not meet inclusion criteria or met an exclusion criterion after signing informed consent
- Surgical intervention that affects the Implantable Pulse Generator (IPG) and/or leads
- Lost to follow-up
- Death of the subject

A subject is considered lost-to-follow-up after 3 unsuccessful contact attempts have been made to reach the subject (including those who relocate but cannot be transferred to another participating site). Staff at the participating site should make a good faith effort to contact the subject with three documented communication attempts, at least one of which must be in writing, sent via a traceable method to inform the subject that the device must programmed per standard of care with commercially approved settings.

Data collected up to the point of subject withdrawal or lost to follow-up may be used for study analysis in accordance with applicable regulations.

Withdrawn subjects will be followed per the End of Study Action Plan as described in Section 10.5.

10.3. *Subject Status and Classification*

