Subjects who provide written informed consent but do not meet all of the study eligibility criteria will not be implanted or activated. These subjects will be deemed as "enrolled but not activated" and their reason for ineligibility will be documented.

Enrolled subjects who are not activated will not count towards the enrollment cap. Subjects who sign consent, meet all eligibility criteria, undergo permanent implant and are activated cannot be replaced.

[REDACTED]

[REDACTED]

[REDACTED]

10.5. *End-of-Study Action Plan*

When each subject completes the 1-Year Visit or withdraws, the subject exits the study and ends study participation. Subjects may continue to use their system per the applicable Directions for Use and will be followed according to standard of care.

If the study is terminated early due to sponsor discretion or due to the discovery of an unexpected, significant, or unacceptable risk/safety concern regardless of how far along the subject has reached in their study follow-up, subjects will be followed according to standard of care. Sites will have 30 days to notify all subjects of study closure.

If device implantation is unsuccessful, the subject will be followed for 2 weeks post implantation attempt to assess for procedure related adverse events. If the device is explanted, the subject will be followed for 30 days post explant to assess for related adverse events.

Device related adverse events and/or deficiencies occurring after study participation, withdrawal from the study, or after the specified timeframe following unsuccessful trials, implant failures, and explants, should be reported to BSN Patient Care at: [contact]. Such complications should not be captured as adverse events in the study.

11. Study Methods

11.1. *Data Collection*

There are a number of different study assessments required at each visit. The data collection schedule is provided in Table 11-1. Full descriptions for all assessments are provided in Section 13.

Table 11.1-1: Data Collection Schedule

| | Screening | Opioid Medication Lock Visit | Baseline Period | Baseline Visit | Implant Procedures (Trial and Permanent) | Activation Visit | Programming Period | Programming Lock Visit | Evaluation Period | 3-Month Visit | 6-Month Visit | 9-Month Visit | 1-Year Visit | Unscheduled Visit |

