11.15. Year 1 Visit (365 ± 30 days)

During the 1 Year Visit, subjects will return to the clinic for study evaluations and programming. Any adverse events since their last study visit will be collected.

The following assessments will be completed as summarized in Table 11.1-1:

- Beck Depression Inventory (BDI-II)
- Oswestry Disability Index version 2.1a (ODI v2.1a)
- Short Form Health Survey 36 items (SF-36 v2)
- EQ-5D 5-Level
- Resource Utilization Inventory (RUI)
- Work Productivity (WPAI-SHP v2.0)
- Pain Intensity: NRS
- Pain Intensity: VRS
- Clinical Global Impression of Change (CGI-C)
- Patient Global Impression of Change (PGI-C)
- Percent Pain Relief (PPR)
- Preference Questionnaire
- Treatment Satisfaction Questionnaire for Medication - modified (TSQM-9m)

Following completion of assessments, subjects' device will be programmed as needed and programming information may be collected.

- In the event of suspected lead migration or to aid programming the subject's device, imaging may be performed to document lead position.
- Any additional instructions related to charging of the device and/or use of Remote Control may be provided.

The 1 Year Visit is the End of Study Visit and End of Study Action Plan (ESAP) will be followed as described in Section 10.5.

11.16. *Unscheduled Visit*

Subjects may have as many unscheduled visits as required for device-related in-office or procedure visits (e.g., optimization of programming during the programming period) or for evaluation of possible adverse events and if applicable, re-positioning, replacement or explant of a device component. Unscheduled visit information will be captured, as applicable.

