11.16.1. Revision or Replacement of Leads, Extensions and/or IPGs

During the course of the study, it is possible that leads may be placed incorrectly, migrate, or malfunction and require repositioning or replacement. It is also possible that the extensions or splitters or IPG may be uncomfortable or malfunction and may require repositioning or replacement. The decision to reposition or replace any device component will be made by the investigator and only if the subject agrees. Subjects not agreeing to a recommended lead revision will be withdrawn from the study but will be included in the intent-to-treat and safety analyses. Subjects agreeing to revision will continue on study and will be followed according to the original study schedule. Effectiveness data from these subjects will be included in the intent to treat analysis. Lead revisions/replacements for the purpose of correcting for migration and/or malfunction must be performed as soon as is reasonably possible following determination of the need for revision/replacement.

The investigator should notify Boston Scientific prior to any study procedures. Any replacements or revisions performed during the course of the study should be recorded in the EDC system, including information about the procedure, device, and/or adverse event if applicable.

Information on assessing revisions or replacements of leads, extensions or IPGs as adverse events is described in Section 20.

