11.18. Study Completion

All activated subjects permanently implanted will be followed through completion of the 1-Year Visit or study withdrawal. The End of Study Action Plan (see Section 10.5) defines the actions to be taken when the subject reaches the end of their study participation.

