19.2. Anticipated Adverse Device Effects

The risks summarized below are anticipated during use of SCS as described in this protocol. The risks listed include those associated with the procedure to implant the SCS device system, the presence of the device (whether activated or not) within the body, and the use of SCS stimulation¹. Potential risks not already identified may exist.

The following anticipated adverse device effects (ADE) have been identified for the SCS device.

Very Common:

- Minor bruising

Common:

- Additional surgical procedure such as explant, revision, or reimplantation of the leads, extensions, or IPG, or revision of the IPG pocket
- Pain, including pain at IPG

¹ Note that some of these symptoms may be resolved or reduced by current steering, changing stimulation parameters, or by repositioning of the lead.

- Stimulation in non-target areas, which can include undesired sensations of pain, pressure, or numbness
- Undesired sensations at stimulation target areas, which can include feelings of pain, pressure, numbness, or dislike of paresthesia
- Overstimulation of tissue, which can include feeling sensations such as jolts or shocks, and potential injuries arising from this causing distraction or loss of muscle control (e.g. fall)

Less Common:

- Infection, such as cellulitis or subcutaneous abscess

Uncommon:

- Discomfort, which can include minor tenderness, uncomfortable awareness of the device, or anxiety
- Skin erosion, including pressure sores, over the device
- Swelling, including seroma, at the IPG site or other locations
- Weight gain or loss

Rare:

- Abnormal healing or failure to heal
- Allergic, immune, or inflammatory response or reaction to the presence of the device or its materials
- Burns due to charger misuse
- Death
- Dural tear with or without Cerebrospinal Fluid (CSF) leak
- Error during implantation of device, e.g. faulty connection of extension to the IPG, which can lead to additional surgery
- Headache
- Hematoma of a serious type, e.g. an epidural hematoma resulting in paralysis
- Hemorrhage requiring transfusion
- Inability to change stimulation, e.g. the remote control stops working
- Infection that is severe or life-threatening, such as epidural abscess, meningitis or sepsis
- Muscle spasms
- Musculoskeletal stiffness

- Nausea
- Nerve injury arising from the electrodes, which can result in symptoms such as unintended tingling, numbness, pain, loss of bladder or bowel control, weakness, or paralysis

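### The plan does not say whether explant ends study participation; if it does, pain and opioid data after explant go uncollected and 6- to 12-month results lean towards subjects who kept the device

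*Combined protocol and SAP*

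**What the plan says.** The End-of-Study Action Plan (Section 10.5) contains the only readable rule for follow-up after explant: "If the device is explanted, the subject will be followed for 30 days post explant to assess for related adverse events". The rule names no pain, opioid or questionnaire assessment. The same section sends device-related events that occur after the post-explant window to the sponsor's patient care line and keeps them out of the study's adverse event data.

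Other sections bear on the same subject:

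- Section 10.5, exit rule: "When each subject completes the 1-Year Visit or withdraws, the subject exits the study and ends study participation". Explant is not named.
- Section 11.18: "All activated subjects permanently implanted will be followed through completion of the 1-Year Visit or study withdrawal".
- Section 10.2 lists reasons for which a subject may be discontinued. One is "Surgical intervention that affects the Implantable Pulse Generator (IPG) and/or leads". The list is permissive, and explant is not named.
- Section 11.16 allows an unscheduled visit for "re-positioning, replacement or explant of a device component" and does not say what happens to the subject's schedule afterwards.
- Section 11.16.1 deals with revision and replacement: "Subjects agreeing to revision will continue on study and will be followed according to the original study schedule". Explant without replacement is not covered.
- Section 13.2.1 collects device- and procedure-related events and all serious events from consent until the study ends.
- Section 10.1 takes every enrolled and activated subject into the analyses.

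The primary objective (Section 6.1) is about "sustained clinically significant pain relief in patients with chronic pain". The primary endpoint is at 3 months; the later pain assessments are at 6, 9 and 12 months.

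**The concern.** A subject whose system has been removed and not replaced is often one in whom the device failed or was not tolerated. If such subjects stop giving pain scores when the device comes out, the scores observed at 6, 9 and 12 months come increasingly from people still using it. A responder rate or mean pain score computed on those scores would then overstate how durable the relief is, and durability is what the word sustained in the objective claims.

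Other parts of the plan make the gap harder to fill. Table 11.1-1 marks opioid medication but neither NRS nor VRS pain for unscheduled visits, so no pain score is required when explant is handled at one. The last score may date from a scheduled visit before relief was lost. Note 6 in Section 20.2 says that lack of efficacy is not reported as an adverse event, so an explant for that reason may leave little trace in the safety data either.

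**Working it through.** **Step 1. Is explant an exit?** The passages point in two directions.

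*Towards exit.* The 30-day rule sits in the end-of-study plan, to which Section 10.2 sends withdrawn subjects. Next to it is a rule of the same form giving a failed implantation 2 weeks of adverse event follow-up, and Section 11.6 says such a subject is then withdrawn. Section 10.5 also closes study capture of device-related events once the explant window has passed. If explanted subjects were still in the study, that would conflict with Section 13.2.1.

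*Against exit.* Section 10.5 names the 1-Year Visit and withdrawal as the points at which participation ends, and its sentence on late events lists explant separately from withdrawal. Section 10.2 permits discontinuation without requiring it. The 30-day rule is an adverse event window and does not say that pain visits stop.

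Both readings leave work to do. If explant is a withdrawal, Sections 10.5 and 11.18 agree but later scores are lost. If it is not, Section 11.18 keeps the visits going, but the adverse event cut-off in 10.5 conflicts with 13.2.1.

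**Step 2. Which visits would be lost under the exit reading?** Visit windows are in days after activation (Sections 11.12 to 11.15).

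- The 6-month window opens on Day 180 − 30 = 150. An explant on Day 100 has its 30 days end on Day 130, so the 6-, 9- and 12-month scores are all missing.
- An explant on Day 130 has its 30 days end on Day 160, so a 6-month visit could still fall inside them.
- The 1-Year window opens on Day 365 − 30 = 335. Any explant before Day 335 − 30 = 305 is out before it opens.
- The 3-month window opens on Day 90. An explant before Day 90 − 30 = 60 would also lose the primary endpoint score.

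**Step 3. How large could the effect be?** The readable text gives no sample size, explant rate or expected 1-year responder rate, so there is no figure of the plan's own to reproduce. Let p be the responder rate among retained subjects, q the rate among explanted subjects, and e the explanted share of activated subjects.

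- Rate over all activated subjects: p(1 − e) + qe
- Rate if explanted subjects leave the denominator: p
- Overstatement: p − [p(1 − e) + qe] = e(p − q), which is p × e when q = 0

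With q = 0 and assumed values of p and e, the rate over all activated subjects (overstatement in percentage points) is:

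| p | e = 2% | e = 5% | e = 10% | e = 15% |
|---|---|---|---|---|
| 0.40 | 0.392 (0.8) | 0.380 (2.0) | 0.360 (4.0) | 0.340 (6.0) |
| 0.60 | 0.588 (1.2) | 0.570 (3.0) | 0.540 (6.0) | 0.510 (9.0) |
| 0.80 | 0.784 (1.6) | 0.760 (4.0) | 0.720 (8.0) | 0.680 (12.0) |

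If some explanted subjects still respond, the figure shrinks. At p = 0.60 and e = 10%, q = 0.30 gives 0.10 × (0.60 − 0.30) = 3 points instead of 6.

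**Step 4. The 3-month endpoint.** The hypotheses in Section 12.1.1.1 put the null boundary at 0.40 − 0.20 = 0.20. With q = 0, a rate of 0.20 over all activated subjects corresponds to a retained-subject rate of 0.20/(1 − e): 0.2105 at e = 5% and 0.2222 at e = 10%. Under these assumptions the shift at the boundary is about 1 to 2 points.

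**The case against.** Three stronger readings are tempting, and the documents do not support them.

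*That Sections 10.5 and 11.18 flatly contradict each other.* Section 11.18 ends follow-up at the 1-Year Visit or at withdrawal. A conflict arises only if an explanted subject is not treated as withdrawn. The defect is an unclassified status.

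*That later pain outcomes come only from subjects who kept the device.* This is an inference. Section 10.5 does not stop pain visits, a visit can fall within the 30 days, and Section 10.2 allows data gathered before withdrawal to be used. Section 10.1 includes all activated subjects, and Section 11.16.1 keeps even subjects withdrawn for refusing a lead revision in the intent-to-treat analysis. Much of Section 12 and the subsection just before 10.5 are blacked out, so a missing-data rule may exist and its absence cannot be counted as a fault.

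*That explant is frequent.* Section 19.2 does list "Additional surgical procedure such as explant, revision, or reimplantation of the leads, extensions, or IPG" as common, but that item pools explant with revision and reimplantation and gives no explant rate. The same section lists infection and skin erosion, so an explant need not mean that relief was lost.

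It is also fair to say that the only readable hypothesis is at 3 months, and that counting explant as non-response is one choice among several.

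What survives is narrower. Membership of an analysis set does not create scores, and a redacted imputation rule could change the denominator but could not recover assessments never made. The readable text leaves sites free to stop assessing explanted subjects, and on balance points them that way.

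**Conclusion.** The point holds as a gap in classification with a plausible bias attached. The plan does not say whether explant is a withdrawal, and the wording of 10.5, read with 11.6, favours treating it as one. On that reading, pain and opioid data after explant are lost selectively, and observed 6- to 12-month results lean towards device keepers.

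The size is unknown. The 2 to 4 points at e = 5%, and the 0.8 to 12 points over the whole table, rest on assumed p and e, on explanted subjects dropping out of the denominator, and on none of them being responders. If the analysis keeps them in as non-responders, this part of the bias disappears from responder rates, though mean pain scores would still lack their data.

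The primary 3-month result is touched only by explants early enough to miss that visit. The change is worth making because it is cheap and protects the durability claim; nothing here shows that the primary conclusion is at risk.

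**What to change.** Reconcile Sections 10.2, 10.5, 11.18 and 13.2.1 so that they give one answer on study status and data collection after explant:

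1. State that explant alone is not withdrawal from the study, and align the adverse event window in 10.5 with the collection period in 13.2.1.
2. State that activated subjects who are explanted and still consent keep the scheduled overall pain (NRS and VRS), opioid and general questionnaire assessments up to 1 Year, with remote collection allowed. Omit items that presuppose a device in use, such as PPR and TSQM-9m.
3. In responder summaries at 3 months and later, keep all activated subjects in the denominator, as Section 10.1 already implies. Report results twice: with subjects explanted without replacement counted as non-responders, and with their observed scores. This is subject to any missing-data rule in the redacted text.

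The cost is a few sentences, one analysis rule and some remote questionnaires for those subjects. Long-term rates may look slightly less favourable.

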11.2. Study Candidate Screening

Subjects' eligibility for the study will be assessed based on study Inclusion and Exclusion criteria listed in Sections 9.2 and 9.3, respectively. Subjects who have provided informed consent and who have been determined to not meet all eligibility requirements will be withdrawn.

11.2.1. Informed Consent

Written Informed Consent must be obtained for all patients who are potential study candidates. Study candidates will be asked to sign the Informed Consent form before any study-specific tests or procedures are performed.

- The context of the study must be fully explained to the patient and patients must be given an opportunity to ask questions and have those questions answered to their satisfaction.
- Study personnel should explain to each potential participant that even if he or she agrees to participate in the study and signs an informed consent form, further testing might demonstrate that he or she is not eligible for the study.
- Written informed consent must be recorded appropriately by means of the subject's dated signature.
- The consent process must be documented in the subject's medical chart.

Research study candidates in the State of California will also be provided with the California Experimental Patient's Bill of Rights

11.2.2. Screening Period

Subjects undergo screening related procedures to determine eligibility for the study. It may take up to the end of Baseline Period to complete all eligibility requirements.

All enrolled subjects who are women of child-bearing potential must undergo a pregnancy test at screening. Women with positive pregnancy test results will be withdrawn from the study. The results of the test result must be documented in the subject's medical chart.

Subjects taking prescription opioids for primary chronic pain complaint (low back and/or leg pain), whose pain medications are not stable for 30 days prior to informed consent, will be withdrawn. However these subjects may be re-consented/rescreened once 30 days have passed since the last change.

Any adverse event occurring after the subject is enrolled (i.e. signing the Informed Consent Form) will be documented.

11.3. Opioid Medication Lock Visit (Up to 35 days following informed consent)

The in-office Opioid Medication Lock Visit will occur within 35 days following informed consent, after completion of some screening requirements as described in Section 11.2. At this visit, the subject's opioid pain medications will be locked, with no change in type/dose/route/frequency, until the 3-Month post-Activation Visit.

At this visit (or during the screening period), the investigator will convert the subject’s opioid medication prescriptions from PRN to a fixed dose, as needed.

11.4. Baseline Period (14 days)

The Baseline Period will last for 14 consecutive days following the Medication Lock Visit. At the end of the Baseline Period, subjects will return to the clinic for their Baseline Visit. Subjects are to not make any changes to their opioid pain medications during this period.

